8.2.1 FACS analysis of PBMCs

To examine treatment induced changes in the quantity and phenotype of circulating immune cells PBMCs will be analyzed by flow cytometry pre-treatment and at two time points post-treatment. Blood samples will be separated into PBMCs and plasma and stored at -80 for batched analysis. PBMCs will be stained for FACS analysis using well characterized antibodies against markers including CD45RA, CD3, CD4, CD8, CD62L, FOXP3, CD25, ICOS, CD127, PD1, PDL1, Tim-3, LAG3, CD56, CD14, CD15, CD16, CD1c, CD11b, CD303, and CD83. Cellular function will be assessed by staining for intracellular cytokines and proliferation using antibodies against Granzyme B, Interferon gamma, tumor necrosis factor (TNF) alpha, and Ki-67. Results will be analyzed using a BD Fortessa multi-color flow cytometer and Flowjo software.

8.2.2 Plasma cytokine / chemokine signatures

To examine treatment induced changes in systemic cytokines / chemokines plasma proteins will be examined pre-treatment and at two time points post-treatment. Markers such as IL-2, IL-6, IL-10, IL-12p70, GM-CSF (granulocyte-macrophage colony-stimulating factor), TNF alpha, IFN (interferon) gamma, CXCL10 (C-X-C motif chemokine 10), RANTES (regulated on activation, normal T cell expressed and secreted), MIP1 (Macrophage Inflammatory Protein) alpha, MIP1 beta and others will be evaluated using the Bio-Rad human 27-plex panel and TGF-beta will be evaluated using the Bio-Rad TGF-beta 3-plex panel. These multi-plexed suspension arrays will be analyzed using a Bio-Plex 200 system and Bio-Plex Manager software.

8.2.3 TCRseq

To examine treatment induced changes in T-cell diversity and clonal expansion and to understand how T-cell clones in the TME relate to circulating T-cells TCRseq will be performed on PBMCs and tumor tissue pre- and post-treatment. For TCR deep sequencing total RNA will be reverse transcribed using SMARTScribe reverse transcriptase (Clontech), a gene specific oligonucleotide, and a template switching oligo to form a universal 5'-adapter. This allows us to amplify the entire diversity of TCR-beta variable chains using just a pair of primers, specific to the template switch oligos on the 5'-end and to the constant gene segments on the 3'-end. Subsequent library amplification is done using Netera XT index kit. Sequencing is performed on the Illumina MiSeq and HiSeq platforms. CDR3 sequences are extracted from raw sequence data and each sequence read is referred to a particular V and J family employing BLAST algorithm. After clustering individual clones (sequence reads with identical V, J and CDR3), virtual CDR3 length spectratyping for each of the V and J gene families is displayed based on the relative amount of each clonal sequence which corresponds to the actual abundance of the T cell clone.

8.2.4 qPCR

Expression levels of immune genes of interest will be assayed pre-and post-treatment within PBMCs and tumor tissue. qPCR will also be used to confirm findings of interest from RNAseq. qPCR will be performed using the StepOnePlus real time PCR system (Life technologies) with primers of interest to examine immune gene signatures of chemokines, cytokines, checkpoint molecules, and others. We will examine genes including, CCL4, Type I IFNs, T-cell markers, IDO, arginase, iNOS (inducible Nitric oxide synthases), CTLA-4, PD-1, PD-L1 and others.

8.2.5 Multi-plex IHC/IF

Immune markers and TILS will be analyzed in tumor tissue pre- and post- treatment. A section of tissue will be formalin fixed and paraffin embedded for multiplex IHC or IF staining and automated analysis in collaboration with [name], director of the Yale translational immuno-oncology laboratory as previously described [60, 61]. We will stain for markers including cytokeratin, CD3, CD4, CD8, CD20, FoxP3, IDO, PD1, PD-L1, Ki67, Granzyme B, IFN and others.

8.2.6 Whole exome sequencing

Genomic DNA will be extracted from baseline PBMC and tumor tissue samples to determine the mutational load of tumor tissues. Whole exome sequencing will be performed at the UC Davis genomics core. Exome capture, sequencing and variant calling: Frozen matched tumor and normal tissue samples will be used to extract at least 2 µg of high quality input gDNA. A fluorometric-based approach will be used for accurate DNA quantification. DNA quality will be assessed and must have a 260/280 nm absorbance ratio of 1.8-2. Extracted DNA will be fragmented using a Covaris S2 System in a 130 µl volume (aim: 400 bp fragments, settings: duty cycle: 10%, intensity: 4, cycles per burst: 200, time: 55s). Size selection, enrichment PCR and library preparation will be performed following manufacturers protocols. Sequencing of barcoded libraries of 150 bp paired ends will be performed on a HiSeq4000 platform in the UC-Davis sequencing facility to an average coverage of 100X. A bioinformatic pipeline will be implemented to identify putative non-synonymous protein coding variants. The process starts by pre-processing sequencing reads to remove sequencing adaptors and low quality sequences using Trimmomatic software package (V 0.36) [62]. Long reads (> 36bp) will be kept and orphans from either paired ends will be pooled in a single file. High quality reads will then be aligned to the human reference genome. Duplicate reads are excluded using the MarkDuplicates module of the Picard software (v2.2.4)[20]. GATK software package allows additional steps of read realignment to minimize mapping artifacts around indels followed by base quality recalibration to adjust for possible systematic technical errors of sequencing quality scoring[63]. Variant calling will be done using four independent variant callers; GATK HaplotypeCaller (v3.5) [63], FreeBayes (v1.2) [64], SAMtools mpileup [65], and VarScan [66]. Different callers apply different algorithms for variant detection e.g., bayesian statistics and local de novo reassembly. An ensemble machine learning pipeline will be used to incorporate results from multiple models [67]. Variants will be annotated using the Variant Annotation Integrator tool of UCSC genome browser [24]. Putative neo-antigens will be cataloged by determining the non-synonymous mutations present in the tumor tissue but absent from the paired PBMCs and their presence in

predicted protein coding sequence. Additionally, indels, copy number variations and structural rearrangements will be cataloged.

8.2.7 RNA sequencing

Tumor tissue pre- and post-treatment will undergo gene expression analysis using next generation sequencing. RNA-seq analysis: mRNA, libraries will be prepared using the TruSeq Stranded mRNA Sample Prep Kit (Illumina). In brief, polyA containing mRNA molecules will be purified from 2 ug of total RNA (RIN >7) from the frozen samples using poly-T oligos attached to magnetic beads. mRNA will then be fragmented to ~300 bp during the polyA elution step. First strand cDNA will be synthesized using SuperScript II reverse transcriptase (Invitrogen) and random primers. After second strand synthesis, cDNA will undergo 3'end adenylation followed by ligation of the indexing adapters. Adapter-ligated DNA will be enriched using 15 cycles of PCR. All purification and size selection steps will be performed using AMPure XP SPRI beads (Beckman Coulter Genomics). Libraries will be validated using the Bioanalyzer High Sensitivity DNA Kit (Agilent Technologies) and quantified on the Eco Real-Time PCR Instrument (Illumina) using KAPA Illumina Library Quantification Kits (KAPA Biosciences) according to the standard manufacturer's protocols. Paired-end cluster generation and sequencing of 2 x 101 cycles will be performed for all libraries on the Illumina Hi-Seq 2000 platform. Short read sequences will be output in FASTQ format with corresponding base quality scores. The raw data will be initially filtered for reads containing ambiguous base calls, which did not meet the Illumina chastity filter based on quality measures. Quality control of the remaining sequences from each sequenced library will be assessed using FastQC to check for adapters, and distribution of base quality. The reads will then be filtered for low quality reads, contaminating 5' adapters, and trimmed for 3' adapters. The pre-processed reads will be aligned using BWA [68] to the hg19 human reference genome Cufflinks [69], then will be used for expression estimation with both bias correction and multi-read correction parameters enabled. Final QC metrics are collected with Picard's CollectRnaSeqMetrics (<http://broadinstitute.github.io/picard>), RSeQC [70], and internally developed scripts. RNA-seq data will be analyzed for somatic variant confirmation and for expression of somatically altered transcripts. Additionally, changes in gene expression profiles pre- and post- treatment will be characterized.

8.3 Responsibilities for Translational Research

All translational research studies described above will be performed by the investigator at the UC Davis Laboratory of cancer Immunology and Human Immune Monitoring Core or in conjunction with collaborating intramural or extramural laboratories. [name] and [name] will oversee all of the studies, data analysis, and data interpretation. Statistical Analysis will be performed by [name].

Merck will be responsible for funding the research as outlined in the research budget and contract. Merck will also be responsible for PD-L1 staining, outside of the multiplexed assay described above, using the IHC 22C3 pharmDx assay.

8.4 All Study Variables

The panel of study endpoints and how they will be measured are described in the below table.

Table 14. Study Variables and Measurements

Endpoint	Variable	Measurement	Comment
Primary- Phase 1	ARR	irRECIST	Objective response at unirradiated sites, the endpoint for measuring responses for the Simon two-stage phase 2 study
Primary- Phase 1	ORR	RECIST and irRECIST	
Primary- Phase 1	DCR	RECIST and irRECIST	
Primary – Phase 1	PFS	RECIST and irRECIST	
Secondary- Phase 1	MTD	CTCAE V4.03	The maximum dose at which <2 of 6 patients experienced a DLT
Secondary- Phase 1	DLT	CTCAE V4.03	Outlined in section 5.4. A DLT is defined as \geq grade 4 injection site reaction OR \geq grade 3 treatment related immunologic adverse event (excluding injection site reactions) OR other \geq grade 3 treatment related adverse events that do not resolve to \leq grade 2 within 14 days of onset during the 30 day DLT period OR Grade 3 diarrhea, AST/ALT $>$ 3 x ULN with bilirubin $>$ 2 X ULN, or pneumonitis that requires holding treatment $>$ 14 days.
Secondary- Phase 2	Safety	CTCAE V4.03	
Translational	PBMC Immunophenotype	FACS	Blood
Translational	PBMC gene expression	qPCR	Blood
Translational	Systemic Cytokine Signature	Luminex	Serum
Translational	Tissue Immune Markers	IHC / IF	Tissue
Translational	Tumor gene expression	qPCR	Tissue
Translational	Mutational load	Whole exome sequencing/ RNA sequencing	Blood and Tissue
Translational	T cell receptor diversity	TCR deep sequencing	Blood and Tissue

9.0 DATA AND STATISTICAL ANALYSIS PLAN

9.1 Sample Size

This is a phase I/II study that will enroll patients with an advanced solid malignancy, or lymphoma to determine if this regimen converts patients with resistance to PD-1/PD-L1 blockade into responders as determined by abscopal response rate (defined as response rate at lesions not treated with RT + IL-2) using irRECIST as well as ORR, DCR, and PFS using RECIST 1.1.

The phase I dose escalation will employ a standard 3 + 3 design with a goal of determining the MTD through DLT assessment. With three dose escalation levels this arm will recruit up to 18 patients.

The Phase II dose expansion will employ a binomial one stage design which will allow us to evaluate if this therapy can convert those resistant to PD-1/PD-L1 blockade into responders. Response will be assessed according to RECIST and will be evaluated at the non-treatment lesions (abscopal response). In order to minimize the required patient numbers, the 3 patients enrolled at the MTD will be included in the phase II efficacy evaluation. We have chosen a threshold of 5% response as not worthy of further evaluation (p0) and a threshold of 20% as worthy of further evaluation in a larger trial (p1). The trial will enroll a total of 21 patients including the three patients treated at the MTD in the phase I (ntot) and must have greater than 3 responders (rtot) for this regimen to be deemed worthy of further evaluation. This design provides a type I error rate of 0.1 and power of 0.82. This trial design will enroll a total maximum of 25 evaluable patients

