2.0 TRIAL DESIGN

Patients with advanced solid malignancies or lymphoma with progression on prior PD-1/L1 blockade will be enrolled. A total maximum of 25 patients will be enrolled.

Primary Objective: Abscopal response rate, ORR, DCR, PFS
Secondary Objective: Maximum tolerated dose (MTD), safety, and toxicity
Collateral Objectives: Immunophenotype serial tumor biopsies and blood samples

Phase I: IL-2 Dose Findin: 3+3 Design: (3-6 patient dose level, 6-18 patients total)				
	Treatment 1 dose	Treatment 2 dose	Treatment 3 dose	Treatment4 dose
Dose Level -1	1 x 10 ⁶ IU	1 x 10 ⁶ IU	1 x 10 ⁶ IU	1 x 10 ⁶ IU
Dose Level 1	3 x 10 ⁶ IU	3 x 10 ⁶ IU	3 x 10 ⁶ IU	3 x 10 ⁶ IU
Dose Level 2	3 x 10 ⁶ IU	7 x 10 ⁶ IU	7 x 10 ⁶ IU	7 x 10 ⁶ IU
Dose Level 3	3 x 10 ⁶ IU	7 x 10 ⁶ IU	15 x 10 ⁶ IU	15 x 10 ⁶ IU

Phase II: IL-2 Dose Expansion Binomial one-Stage Design (18 additional patients; analyzed with patients from MID)	

 P= 0.05, p1= 0.20, r1= 0, n1= 10, rTot=3, nTot=21, a= 0.1, power=0.8 Response will be assessed according to irRECIST and will be evaluated at the non-treatment lesions (abscopal response) 	

CT= computed tomography, DCR=disease control rate, MTD=maximum tolerated dose, ORR=objective response rate, PFS=progression free survival, RT=radiotherapy, P=pembrolizumab,

- a. Patients will be clinically evaluated prior to each cycle of pembrolizumab for the first 3 cycles and weekly during intralesional IL-2 injections, and thereafter every 3 cycles until off treatment.
- b. Laboratory evaluation will occur pre-treatment at every cycle.
- c. For response assessment, patient will have CT imaging pre-treatment and after every three cycles of pembrolizumab.

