5.2 Trial Treatments

This is a phase I/II study that will evaluate the safety and toxicity of this combinatorial approach. Eligible patients ≥ 18 years of age with histologically proven advanced solid malignancy or lymphoma who have failed PD-1 / PD-L1 checkpoint blockade therapy will be enrolled. Patients must have a candidate treatment lesion accessible and safe for radiotherapy and serial intralesional injections as specified by the protocol. They must also have at least one target lesion (distinct from treatment lesion and outside of treatment lesion radiation field) evaluable for response by RECIST.

This study will consist of a phase I dose escalation / de-escalation using a standard 3+3 design to determine safety and MTD of intralesional IL-2 which will be dose escalated in conjunction with standard fixed doses of RT and Pembrolizumab. The study will begin at dose level 3 and the dose will be de-escalated if needed to determine the MTD. At the MTD there will be a phase II dose expansion which will incorporate a simon-two stage design to assess efficacy and safety.

Patients will receive pembrolizumab and intralesional IL-2 in combination with hypofractionated radiotherapy.

- Radiotherapy will be delivered to the treatment lesion during the second cycle of therapy using an 8 Gy x 3 fractions palliative regimen. Fractions may be delivered on consecutive days or every other day but must be completed during weeks 1-2 of cycle 2 and will not be repeated in future cycles.
- Pembrolizumab will be delivered at 200 mg in three-week cycles .

- A total of four interleukin-2 treatments will be delivered into the treatment lesion by intralesional injection biweekly (at least 48 hours apart) starting 24-96 hours after the completion of radiotherapy and to be completed during the second on-trial cycle of Pembrolizumab. Intralesional injections will be performed by direct visualization and/or palpation of the lesion or under ultrasound or CT guidance as indicated. Intralesional IL-2 injections will follow guidelines which we have previously published [46]. IL-2 will be administered at three dose levels: 1) 3×10^6 IU, 2) 7×10^6 , 3) 15×10^6 IU. The study will begin at dose level 3 and the dose will be de-escalated as needed to establish the MTD.

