9.4 Efficacy

As an exploratory endpoint, all responses will be reported using RECIST 1.1 definitions [58]. Because of the potential heterogeneity of the patients, all results will be considered preliminary and hypothesis generating for future studies. Response rate among will be summarized by exact binomial confidence intervals. Disease free survival will be summarized with Kaplan-Meier plots to describe the outcome of patients treated on this protocol. The median DFS time will be estimated using standard life table methods.

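### The phase II success rule in Section 9.1 (more than 3 responders of 21) has power 0.63, not the stated 0.82; 0.82 is the power of at least 3 of 21

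*Combined protocol and SAP*

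**What the plan says.** Section 9.1 describes the phase II expansion as a one-stage binomial design. The uninteresting response rate is 5%, the rate worth pursuing is 20%, and 21 patients are analysed, three of them carried over from phase I. The decision rule is that the trial "must have greater than 3 responders (rtot) for this regimen to be deemed worthy of further evaluation". Its operating characteristics follow directly: "This design provides a type I error rate of 0.1 and power of 0.82". The same section limits enrolment: "This trial design will enroll a total maximum of 25 evaluable patients".

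The design table in Section 2.0 gives the parameters as "P= 0.05, p1= 0.20, r1= 0, n1= 10, rTot=3, nTot=21, a= 0.1, power=0.8". It does not say whether 3 responders is the largest failing count or the smallest passing count, so Section 9.1 is the only place where the rule is put into words.

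Section 9.4 adds that "all results will be considered preliminary and hypothesis generating for future studies".

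**The concern.** The rule and its power sit in adjacent sentences and cannot both be right. For so small a trial, moving the cut-off by one responder changes the power substantially, so the wording decides which test is being run.

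This is the only efficacy rule in the plan with stated error rates, and abscopal response is the first primary objective in Section 3.1. If exactly 3 of 21 patients respond, the text says stop and the stated power implies go. The trial is open-label, so anyone settling that conflict afterwards would already know the responses. No confirmatory claim depends on it. What is at risk is the decision on whether a larger trial is warranted.

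**Working it through.** **Inputs (Section 9.1; repeated in Section 2.0).** n = 21, p0 = 0.05, p1 = 0.20. Stated type I error 0.1, stated power 0.82. The power in Section 2.0 is given as 0.8.

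**Formula.** For a rule that succeeds with at least r responders, P(success) = 1 − Σ C(21,k) p^k (1−p)^(21−k), summed over k = 0 to r−1. At p0 this is the type I error; at p1 it is the power.

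**Binomial terms for n = 21**

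| k | P(X = k), p = 0.05 | P(X = k), p = 0.20 |
|---|---|---|
| 0 | 0.3406 | 0.0092 |
| 1 | 0.3764 | 0.0484 |
| 2 | 0.1981 | 0.1211 |
| 3 | 0.0660 | 0.1917 |

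**Reproducing the stated power: at least 3 of 21**
- Power = 1 − (0.0092 + 0.0484 + 0.1211) = 0.8213, which matches 0.82.
- Type I error = 1 − (0.3406 + 0.3764 + 0.1981) = 0.0849.

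**Rule as written: more than 3, that is at least 4 of 21**
- Power = 0.8213 − 0.1917 = 0.6296.
- Type I error = 0.0849 − 0.0660 = 0.0189.

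The shortfall in power is 0.192, exactly the probability of 3 responders at a 20% rate. The chance of rejecting a regimen with a true 20% rate is 1 − 0.6296 = 0.370, against 1 − 0.8213 = 0.179 under the stated power.

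**Which cut-off does the sample size fit?** A search over all n and cut-offs for type I error ≤ 0.10 and power ≥ 0.80 finds n = 21 with at least 3 as the smallest one-stage design. At n = 20, at least 3 gives power 0.794.

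**Could more than 3 reach the stated power at another n?** At n = 25, the enrolment cap, its power is 0.766 (type I error 0.034). It first passes 0.80 at n = 27 (power 0.818, type I error 0.044).

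**Could a two-stage design explain 0.82?** Section 2.0 still lists r1 = 0 and n1 = 10. Stopping after 0 responders in 10 and otherwise continuing to 21 gives:
- at least 3 of 21: type I error 0.076, power 0.780;
- more than 3 of 21: type I error 0.018, power 0.612.

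Neither gives 0.82.

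**Conditional figures if the efficacy n is not 21.** These are scenarios, not designs the plan states.
- Six MTD patients plus 18 more gives n = 24: type I error/power 0.116/0.886 (at least 3) or 0.030/0.736 (more than 3).
- If dose level 3 is rejected after six patients, the cap leaves 25 − 6 = 19: power 0.763 (at least 3) or 0.545 (more than 3).
- If it is rejected after three patients, 25 − 3 = 22 places remain and 21 still fits.

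**The case against.** **The intended cut-off is not proven.** In Section 2.0 a first-stage r of 0 makes sense only as a largest failing count. Read in parallel, 3 is also a failing total, which agrees with the words in Section 9.1. So the wording and this notation point to more than 3, while the sample size and power point to at least 3. This stands: the documents establish a contradiction, not which side was meant.

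**The 0.1 may be an attained rate.** Section 9.1 says the design provides it. If it is an attained rate, neither cut-off gives it exactly (0.085 or 0.019). Read as a ceiling, both respect it. Either way the power is wrong for the written rule.

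**The consequence is limited.** Section 9.4 treats all results as preliminary, the rule guides no patient's treatment, and the two cut-offs differ at one outcome only. That is true. But the rule exists to decide whether a larger trial is justified, and that one outcome has probability 0.192 at the rate the trial hopes to detect.

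**The scenarios at n = 24 and n = 19 are side issues.** Sections 2.0 and 9.1 both fix 21, and other dose-finding paths could leave other numbers. This is fair, and the main finding does not depend on them.

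**Conclusion.** The concern holds. With n = 21, 5% against 20%, and an exact one-stage binomial test, the rule as written has power 0.63 and type I error 0.019. The stated power of 0.82 is that of at least 3 of 21, whose type I error is 0.085. The overstatement is 19 percentage points, and the chance of discarding a regimen with a true 20% rate is about double what the plan implies (37% against 18%). Every input comes from Section 9.1. The only reading adopted is that 0.1 is a nominal ceiling, and the power error does not depend on it.

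Two consistency points are secondary:
- Section 5.2 still announces a "phase II dose expansion which will incorporate a simon-two stage design to assess efficacy and safety" and Table 14 in Section 8.4 calls abscopal response "the endpoint for measuring responses for the Simon two-stage phase 2 study", while Sections 1.0, 2.0 and 9.1 say one-stage.
- Section 9.1 says that "the 3 patients enrolled at the MTD will be included in the phase II efficacy evaluation". That fits if level 3 goes forward after 0 of 3 with DLT, but it does not cover the six-patient MTD cohort also described in Section 5.4.1.1, Table 4 and Table 14.

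**What to change.** State one cut-off, with its exact figures, in Sections 9.1 and 2.0. Either:
- the regimen is worthy of further evaluation if at least 3 of 21 patients have an abscopal response (exact type I error 0.085 at 5%, power 0.82 at 20%); or
- keep more than 3 of 21 and restate type I error 0.019 and power 0.63.

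Take the choice from the original design output, without reference to observed responses, and record that this was done. This matters most for at least 3, which lowers the bar for success in an open-label trial. Keeping more than 3 means accepting power 0.63, because 27 patients would exceed the cap.

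For consistency:
- Once it is confirmed that no interim futility stop is intended, delete r1 and n1 from Section 2.0 and replace the Simon two-stage wording in Section 5.2 and Table 14 with one-stage binomial. If a stop is intended, the one-stage figures above do not apply.
- State that the efficacy n stays 21 if six phase I patients were treated at the MTD (21 − 6 = 15 additional rather than 18), and give the power if the cap leaves only 19.

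The cost is an amendment to the text of Sections 2.0, 5.2, 8.4 and 9.1, with the supporting company's and IRB approval under Section 11.5. Neither option adds patients.
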